4.5.9 Lung Biopsy

Lung biopsies are not required for eligibility into the study *and are not required during the study.* Patients who have undergone a lung biopsy (including cryobiopsy) to support the diagnosis of IPF, should have the relevant slides sent for central review assessment to confirm eligibility in accordance with the ATS/ERS/JRS/ALAT IPF Clinical Practice Guideline (Raghu et al. 2018). The central review pathologists will evaluate submitted slides for UIP pattern. The histopathologic assessment criteria are outlined in [Appendix 10](#).

4.5.10 Assessment of Acute Exacerbations of IPF, Hospitalizations for Respiratory Causes, and Deaths (Adjudicated Events)

An independent, blinded *Clinical* Adjudication Committee will be convened to review all available data for all potential cases of acute exacerbations of IPF, hospitalizations for respiratory causes, and all deaths. This *Clinical* Adjudication Committee will be comprised of pulmonary disease physicians familiar with IPF exacerbations. A charter for the *Clinical* Adjudication Committee will provide further details. The *Clinical* Adjudication Committee will determine if the reported events meet the criteria of acute exacerbation of IPF, hospitalization for respiratory causes, and deaths (including deaths related specifically to respiratory causes) as defined in the charter.

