4.5.10.3 Deaths Due to Respiratory Causes

All deaths occurring during the study must be recorded. The event or condition that caused or contributed to the fatal outcome should be recorded as a single medical concept on the Adverse Event eCRF.

All investigator-reported deaths will be assessed by an independent *Clinical* Adjudication Committee to determine whether each death was related to IPF, another respiratory cause, or an alternative (non-respiratory and non-IPF) cause.

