1.2.2.3 Lung Biopsy

Lung biopsies are not required for eligibility into the study. Patients who have undergone a lung biopsy (including cryobiopsy) to aid in the diagnosis of IPF, should have slides sent for central review assessment to confirm eligibility in accordance with the ATS/ERS/JRS/ALAT Clinical Practice Guideline ([Raghu et al. 2018](#)). The central review pathologists will evaluate submitted slides for usual interstitial pneumonia (UIP) pattern. The histopathologic assessment criteria are outlined in the Protocol.

1.2.2.4 Assessment of Acute Exacerbations of IPF, Hospitalizations for Respiratory Causes, and Deaths (Adjudicated Events)

An independent, blinded Clinical Adjudication Committee will be convened to review all available data for all potential cases of acute or suspected exacerbations of IPF, hospitalizations for respiratory causes, and all deaths. This Clinical Adjudication Committee will be comprised of pulmonary disease physicians familiar with IPF exacerbations. A charter for the Clinical Adjudication Committee will provide further details. The Clinical Adjudication Committee will determine if the reported events meet the criteria of acute or suspected exacerbation of IPF, hospitalization for respiratory causes, and deaths (including deaths related specifically to respiratory causes) as defined in the charter.

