4.1 GENERAL CONSIDERATION

The efficacy endpoints comprise one primary endpoint (FVC [mL]), one key secondary endpoint (6MWD [m]), a series of other secondary endpoints and other exploratory endpoints. All efficacy analyses will be performed on the FAS population, unless otherwise specified. Participants will be analyzed according to the treatment assigned at randomization by IxRS. Significance testing of the primary and secondary endpoints will account for multiplicity and control family-wise type I error, which is fixed at 0.05 two-sided. All safety analyses will be performed in the safety-evaluable population, unless otherwise specified. Participants will be analyzed according to the treatment they actually received.

In safety analyses, all deaths are included, from all sources, regardless of completeness of death date; participants who died with only a partial death date available will be included. In efficacy analyses, death data from adjudication will be used. If the death date is only partially available, the missing part of the date will be imputed.

For hospitalization in efficacy analyses, the adjudicated date of hospitalization will be used and a partial date will be imputed using the same approach as for death.

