4.4.2.3 Time-to-Event Secondary Endpoints

The time-to-event secondary endpoints are listed below:

- Time to disease progression, defined as time to first occurrence of $\geq 10\%$ absolute decline in % predicted FVC, $\geq 15\%$ relative decline in 6MWD, or death
- Time to first respiratory-related hospitalizations (defined as non-elective hospitalizations due to any respiratory cause, including acute exacerbations of IPF, or suspected acute exacerbations of IPF, as determined by the Clinical Adjudication Committee)
- Time to first acute exacerbation of IPF, or suspected acute exacerbation of IPF, as determined by the Clinical Adjudication Committee
- Survival, as measured by all-cause mortality

Descriptive statistics for the frequency of each type of event will be provided. The stratified log rank test (on stratification factors) will be used to compare the time to event endpoints between two treatment arms at a 0.05 two-sided significance level. The Kaplan-Meier plot, median time to event, and their 95% CIs, and a p-value from the log-rank test will be presented. The hazard ratio and its 95% CI will be estimated using a Cox proportional hazards model, adjusting for sex, age, and height. In fitting the Cox model, ties will be handled with the approximate likelihood method of Efron (1977).

Time-to-event will be measured in reference to Baseline Day 1 through the end of study. Patients are considered to be in the placebo-controlled period even if they have discontinued study treatment, if they would still be receiving placebo-controlled study treatment had they not discontinued. For time to first respiratory-related hospitalizations and time to first acute exacerbation of IPF, patients not experiencing an event will be censored at the earliest of the last day known alive, or the last date during the placebo-controlled period (see Section 1.2). For disease progression and survival (all-cause mortality), patients without an event will be censored at the last clinic assessment during the placebo-controlled period.

The estimand strategy for the time-to-event endpoints are summarized below in Table 7.

**Table 7 Estimand Analysis Strategy for Intercurrent Events:
Time-to-Event Secondary Endpoints**

Endpoints	Estimand

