
 Time to disease progression, defined as time to first occurrence of $\geq 10\%$ absolute decline in % predicted FVC, $\geq 15\%$ relative decline in 6MWD, or death 	
Population: see primary endpoint Treatment: see primary endpoint Population-level summary measure: log rank test and hazard ratio Intercurrent events:
 
 Any patients who undergo lung transplantation will be censored at the date of the transplant (hypothetical strategy)

 Survival, as measured by all-cause mortality 	
Population: see primary endpoint Treatment: see primary endpoint Population-level summary measure: log rank test and hazard ratio Intercurrent events:
 
 Any patients who undergo lung transplantation will be censored at the date of the transplantation (hypothetical strategy)

 Time to first respiratory-related hospitalizations (defined as non-elective hospitalizations due to any respiratory cause, including acute exacerbations of IPF, or suspected acute exacerbations of IPF, as determined by the Clinical Adjudication Committee) 	
Population: see primary endpoint Treatment: see primary endpoint Population-level summary measure: log rank test and hazard ratio Intercurrent events:
 
 Deaths are expected to be infrequent, but in case of occurrence, they will be treated as disease progression and counted as event of interest (composite strategy) Any patients who undergo lung transplantation will be censored at the date of the transplantation (hypothetical strategy)

 Time to first acute exacerbation of IPF, or suspected acute exacerbation of IPF, as determined by the Clinical Adjudication Committee 	
Population: see primary endpoint Treatment: see primary endpoint Population-level summary measure: log rank test and hazard ratio Intercurrent events:
 
 Deaths are expected to be infrequent, but in case of occurrence, they will be treated as disease progression and counted as event of interest (composite strategy) Any patients who undergo lung transplantation will be censored at the date of the transplantation (hypothetical strategy)

6MWD = 6-minute walk distance; FVC = forced vital capacity; IPF = idiopathic pulmonary fibrosis.

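### SAP 4.4.2.3 pairs its two censoring dates with the wrong time-to-event endpoints: survival stops at the last clinic visit, while hospitalisation and exacerbation run to the last day known alive

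*SAP*

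**What the plan says.** SAP 4.4.2.3 sets two censoring rules for patients without an event.

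- Survival and disease progression: "For disease progression and survival (all-cause mortality), patients without an event will be censored at the last clinic assessment during the placebo-controlled period".
- First respiratory hospitalisation and first acute exacerbation: patients are "censored at the earliest of the last day known alive, or the last date during the placebo-controlled period". Table 7 also counts death as an event for these two endpoints.

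The placebo-controlled period is Day 1 to Week 52 (SAP 1.2). Events, however, have a different horizon: "Time-to-event will be measured in reference to Baseline Day 1 through the end of study". End of study is Week 52 or Week 56, depending on entry to the extension (Protocol Table 1).

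On deaths, SAP 4.1 says "In efficacy analyses, death data from adjudication will be used" and sets no limit relative to the last visit. The adjudication committee reviews "acute or suspected exacerbations of IPF, hospitalizations for respiratory causes, and all deaths" (SAP 1.2.2.4). Protocol 4.5.10 and 9.5 also cover every death, but Protocol 4.5.10.3 is narrower: "All investigator-reported deaths will be assessed by an independent" committee.

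Protocol 5.3.4 allows survival data by telephone or electronically. After loss to follow-up or withdrawal it uses death registries where approved and available, unless consent for this is withdrawn. Exacerbations are sought by questions and file review at study visits (4.5.10.1), and the hospitalisations adjudicated are those the investigator reports (4.5.10.2). Adverse events are reported until 8 weeks after the last dose (5.4.1). After that, only serious events thought related to study drug are requested (5.7).

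**The concern.** A censoring date should be the last date on which the endpoint's event would have been known had it occurred. Death can be known without a visit, yet survivors are cut at the last visit. Time between that visit and a later known-alive date is discarded for survivors and kept for those who die, so follow-up depends on outcome.

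Hospitalisation and exacerbation need to be asked about or reported. Survival-only information keeps the patient in the risk set when such events could not be seen, so incidence is understated.

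The two errors run in opposite directions. An arm with more withdrawal would show too many deaths and too few hospitalisations or exacerbations, which could be mistaken for a clinical pattern. At stake are secondary endpoints 4, 7 and 9 in the SAP 4.4 order, and endpoint 3 slightly. Protocol 6.5.4 says later tests are computed even after the sequence stops, so these results will be reported either way.

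**Working it through.** **The plan's own figures.** SAP 2.2 gives power only for FVC (mL), 6MWD and FVC % predicted. The FVC figure reproduces: 0.25 × √(329/2) = 3.21; 3.21 − 1.96 = 1.25; power 0.89. No event rate or hazard ratio is given for any time-to-event endpoint, so the size below rests on assumptions.

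**Sources set against censoring dates.**

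| Endpoint | How the event becomes known | Censoring date as written |
|---|---|---|
| Survival | visit, call, electronic contact, registry | last clinic assessment |
| Hospitalisation, exacerbation | visit, investigator report, call asking about adverse events | last day known alive, at most Week 52 |

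**Assumed inputs.** One-year death 8%, respiratory hospitalisation 15%, constant hazards, no treatment effect. A proportion w leaves, uniformly over 52 weeks, and visits are 4-weekly. Yearly hazards: death −ln 0.92 = 0.0834; hospitalisation −ln 0.85 = 0.1625; together 0.2459. Full tracing means vital status is known for every leaver to Week 52.

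**Survival, full tracing.** Deaths per patient are 0.08. True person-time is 0.08/0.0834 = 0.9594 years. A surviving leaver is cut at the last visit, on average Week 24 (mean leaving week 26, minus 2), losing 28/52 = 0.5385 years.

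Person-time(w) = 0.9594 − w × 0.92 × 0.5385

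- w = 10%: 0.08/0.9099 = 0.0879, read as 8.4% mortality
- w = 20%: 0.08/0.8604 = 0.0930, read as 8.9%
- w = 25%: 0.08/0.8356 = 0.0957, read as 9.1%

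Ratios: 10% v 20%, 0.0930/0.0879 = 1.06; 10% v 25%, 0.0957/0.0879 = 1.09. With matched censoring both arms give 0.08/0.9594, ratio 1.00.

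**Survival, half tracing.** A traced leaver contributes 0.08 deaths and 0.4641 years. An untraced leaver contributes 1 − 0.9594 = 0.0406 deaths and 0.0406/0.0834 − 0.9594 × 2/52 = 0.4495 years.

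- w = 10%: (0.9×0.08 + 0.05×0.08 + 0.05×0.0406)/0.9092 = 0.0858
- w = 25%: (0.75×0.08 + 0.125×0.08 + 0.125×0.0406)/0.8338 = 0.0900

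Ratio 1.05. With no tracing, mortality reads 8.0–8.1% and there is no material bias.

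**Hospitalisation or death, full tracing.** The true risk is 1 − 0.92 × 0.85 = 21.8%. A patient who stays contributes 0.218 events and 0.218/0.2459 = 0.8865 years. After a patient leaves, only death is visible, but the patient stays at risk. A leaver therefore contributes 1 − 0.92 × (0.15/0.1625) = 0.1509 events, and (1 − 0.8865)/0.2459 + (0.8865 − 0.8491)/0.0834 = 0.4614 + 0.4486 = 0.9100 years (0.8491 = 1 − 0.1509).

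- w = 10%: 0.2113/0.8889 = 0.2377, read as 21.2%
- w = 25%: 0.2012/0.8924 = 0.2255, read as 20.2%

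Ratio 0.95. With half tracing, an untraced leaver contributes 0.1135 events and 0.4614 − 0.8865 × 2/52 = 0.4273 years. The rates are 0.2094/0.8647 = 0.2422 and 0.1966/0.8320 = 0.2362, ratio 0.98.

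Simulation under the same assumptions agrees to within 0.1 percentage points on the curves, and on all these hazard ratios to two decimals. With 3% one-year mortality the survival ratio at 10% v 25% is still 1.09–1.10.

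**If an empty registry search is taken as proof of life.** Suppose the search finds a fraction d of deaths after leaving, and missed deaths are carried as alive to Week 52. A leaver contributes 0.0406 + d × 0.0394 deaths, plus (1 − d) × 0.0133 years of false survival time (0.0133 is the average time from an unseen death to Week 52, per leaver). At d = 50%:

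- w = 25%: 0.0751/0.9611 = 0.0781
- w = 10%: 0.0780/0.9601 = 0.0813

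Ratio 0.96, so the bias reverses.

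**The case against.** Much of the opposing case stands.

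- Calls that replace a missed visit are meant to collect adverse events (Protocol 5, opening text). Hospitalisations are serious events (5.4.5.11), exacerbations are events of special interest (5.3.3), and both are reportable until 8 weeks after the last dose. A reader might infer that any known-alive date is uninformative about these events. The documents do not support that; the gap concerns mainly survival-only contacts, chiefly after that window.
- The SAP does not say that an empty registry search supplies a known-alive date. Without such a rule, leavers with registry data only are censored at their last actual contact, and the hospitalisation bias does not arise for them.
- Full tracing is a ceiling. Registries are conditional on approval and consent, and survival follow-up of leavers is offered through a separate study, WA42294, whose data are not said to enter this analysis.
- Patients who stop drug are expected to keep attending (Protocol 4.6), so they are little affected.
- The adjudication wording is a small conflict: three sections cover every death, and only Protocol 4.5.10.3 needs an edit.

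None of this removes the survival mismatch.

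A reader might also infer that family-wise error or the main conclusion is at risk. It is not: the primary and key secondary endpoints are not time-to-event, and each later endpoint is formally tested only after all earlier ones succeed. Nor do disease progression or the Week 52/56 difference add a material bias. FVC and 6MWD are scheduled at every 4-weekly visit, and the simulated progression hazard ratio was 1.01. A death in Weeks 53–56 with nobody else at risk distorts the curve but adds nothing to the log-rank test (observed 1, expected 1, variance 0).

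**Conclusion.** The two rules are mismatched as written, and the SAP should be changed. The survival rule overstates mortality whenever deaths after the last visit are counted. The hospitalisation and exacerbation rule understates incidence for patients known only to be alive.

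At 10% v 25% withdrawal and the assumed event rates, the null hazard ratio is about 1.09 for survival and 0.95 for hospitalisation or death as a ceiling, and about 1.05 and 0.98 with half tracing. In simulated trials of 329 per arm, the per-endpoint type I error in that setting was about 6% with full tracing. It was 4.8–5.4% with half tracing, and runs at 10% v 20% withdrawal showed no consistent inflation, so the point does not rest on type I error.

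With equal withdrawal the hazard ratio is not biased, although the curves in both arms still are. Withdrawal, event and tracing rates are all assumptions.

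**What to change.** 1. **Survival.** Count adjudicated deaths from any source up to Week 52. Censor at the earlier of the last date known alive from any documented source and Week 52. Use a registry search that finds no death as a known-alive date only where the registry's coverage is considered complete to that date. Otherwise apply the same ascertainment cut-off to deaths and survivors, for example by leaving registry-only deaths out of the main analysis, and show the other handling as a sensitivity analysis.
2. **Hospitalisation and exacerbation.** Censor at the earlier of the last contact (visit or call) at which these events were assessed and Week 52. State one rule for deaths after that contact, with a sensitivity analysis under the alternative rule.
3. **Cut-off and adjudication.** Use one Week 52 cut-off for events and censoring. Align Protocol 4.5.10.3 with the sections that send every death to adjudication.

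For tidiness only, tie censoring for disease progression to the last accepted FVC and 6MWD assessment.

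The cost is a few SAP sentences before unblinding and one protocol wording edit. The fix adds no visits or assessments, but someone must judge registry coverage, and the data must show which contacts asked about hospitalisation and exacerbation.

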4.5 EXPLORATORY ENDPOINT(S) ANALYSIS

The exploratory efficacy endpoints are:

- Absolute change from baseline at Week 52 in FVC% predicted and FVC (mL), by baseline concomitant medication stratum
- Absolute change from baseline at Week 52 in FVC% predicted and FVC (mL), by mucin 5B (MUC5B) risk allele positive or negative status
- Absolute change from baseline at Week 52 in 6MWD (m), by baseline concomitant medication stratum
- Proportion of patients who progress on the UCSD-SOBQ, as indicated by an increase in score of 10 points or greater
- Proportion of patients who progress on the SGRQ total score, as indicated by an increase in score of 7 or greater
- Change from baseline to Week 52 in SGRQ Individual Domains (Symptoms, Activity, and Impacts) Score
- Proportion of patients who progress on the SGRQ Symptoms Domain, as indicated by an increase in score of 8 or greater
- Proportion of patients who progress on the SGRQ Activity Domain, as indicated by an increase in score of 5 or greater
- Proportion of patients who progress on the SGRQ Impacts Domain, as indicated by an increase in score of 7 or greater
- Absolute change from baseline at Week 52 in quantitative imaging analysis parameters of HRCT scan of the thorax
- Length of hospital stay for respiratory-related hospitalizations
- Total time in intensive care units due to respiratory causes
- Unscheduled outpatient clinic/urgent care/emergency room utilization related to respiratory events
- Number of acute exacerbations during the 52 weeks, as determined by the Clinical Adjudication Committee
- Survival as measured by IPF-related mortality
- Survival as measured by respiratory-related mortality
- Disease progression and subsequent start of oxygen supplementation
- Change in PFT parameters (FVC, DL_{CO}) or 6MWD from baseline at Week 52 between SARS-CoV2 antibody positive compared with negative patients (present at baseline)
- Change in PFT parameters (FVC, DL_{CO}) or 6MWD from baseline at Week 52 in patients who develop SARS-CoV2 antibodies during treatment (not present at baseline)
- Absolute change from baseline at Week 52 in FVC (mL) by selected countries

In addition, the following endpoint will be explored to evaluate health status utility scores of patients treated with zinpentraxin alfa plus standard of care treatment:

- Absolute change from baseline at Week 52 in EuroQol 5-Dimension, 5-Level Questionnaire (EQ-5D-5L) index-based, and visual analog scale (VAS) scores

Change-from-Baseline Exploratory Endpoints: FVC, 6MWD, DL_{CO}, EQ-5D-5L VAS

The endpoints on FVC, 6MWD and DL_{CO} will be analyzed and summarized with use of the same methods as the change from baseline endpoints in Section 4.3.2, Section 4.4.1, and Section 4.4.2.1, unless otherwise specified.

The EQ-5D-5L VAS endpoint will be analyzed and summarized with use of the same methods as the change from baseline endpoints in Section 4.4.2.2.

Change-from-Baseline Exploratory Endpoints: HRCT

Descriptive statistics for the raw values at each visit and the change from baseline to Week 52 will be computed by the treatment group for the quantitative HRCT imaging analysis parameters.

Proportion of progressors: SGRQ, UCSD-SOBQ

The proportion of progressors at Week 52 will be estimated by treatment group with 95% CIs using a standardized regression estimator, adjusting for baseline score and baseline concurrent IPF treatment.

Acute Exacerbation of IPF Endpoints

Descriptive statistics for continuous variables will be prepared by treatment group for the total number and rate (per year) of acute or suspected exacerbations during the 52 weeks.

Time-to-Event Exploratory Endpoints

These endpoints will be analyzed and summarized with use of the same methods for the time-to-event secondary endpoints, unless otherwise specified.

Healthcare Utilization Exploratory Endpoints

Descriptive statistics for continuous variables will be prepared for:

- Length of hospital stay in days for respiratory-related hospitalizations
- Total time in intensive care units in days due to respiratory causes

- Unscheduled outpatient clinic/urgent care/emergency room utilization related to respiratory events

Impact of SARS-CoV2 Antibody

Descriptive statistics will be prepared for:

- Change in PFT parameters (FVC, DL_{CO}) or 6MWD from baseline at Week 52 between SARS-CoV2 antibody positive compared with negative patients (present at baseline)
- Change in PFT parameters (FVC, DL_{CO}) or 6MWD from baseline at Week 52 in patients who develop SARS-CoV2 antibodies during treatment (not present at baseline)

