 - Death: Deaths are expected to be rare as the study plans to include patients with a life expectancy longer than the study duration. Given that deaths are expected to be rare, and the observation that conservative imputation of missing, post-death data for continuous FVC (mL) outcomes introduces highly influential outliers, deaths will be treated with a hypothetical strategy. A sensitivity analysis described in Section 4.3.3.1.1 will assess the impact of this strategy on treatment effect estimation and inference.
 - Lung transplantation: Lung transplantation is expected to be rare during the study, as patients likely to receive a lung transplantation during the study are excluded. Furthermore, the treatment effect of interest is in the hypothetical scenario that lung transplantations are unavailable, since assessments following lung transplantation are no longer reflective of diseased lung(s).

In some instances, FVC can improve to over 80% following lung transplantation, or even 100% for bilateral lung transplantation 6-12 months after surgery (Hernandez et al. 2018). Therefore, any data recorded after lung transplantation will be excluded from the analysis and treated as missing data because such data is not compatible with this hypothetical strategy.

- Hospitalization for COVID-19: The treatment effect of interest is irrespective of COVID-19 hospitalization, given that COVID-19 hospitalizations will likely continue for the population of interest for the foreseeable future. Therefore, all data recorded after COVID-19 hospitalization will be included in the analysis. Any missing data after COVID-19 hospitalizations will be assumed to be MAR.

In general, with the exception of data collected after lung transplantation, all observed outcome data will be included in the analysis. All missing data, including data excluded after lung transplantations and missing data due to death, will be considered similar to data from other patients in the same treatment group with the same baseline characteristics with no such missing data (compatible with MAR assumption). Sensitivity analyses addressing missing data assumptions are described in Section 4.3.3.

Table 2 below summarizes the handling of intercurrent events for the primary estimand.

Table 2 Primary Estimand Analysis Strategy for Intercurrent Events

Intercurrent Event (ICE)	Analysis strategy	
Any change to randomized treatment	Temporary study drug discontinuation	Treatment policy

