4.4.2.2 PRO Secondary Endpoints

The PRO secondary endpoints are listed below:

- Change from baseline at Week 52 in UCSD-SOBQ score
- Change from baseline at Week 52 in SGRQ total score

The PRO secondary endpoints will be analyzed using the same estimand strategy, descriptive statistics and model as Hgb-corrected DL_{CO} % predicted in Section 4.4.2.1 and will be analyzed at a 0.05 two-sided significance level.

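### The SGRQ and UCSD-SOBQ progressor proportions leave the Week 12 to 36 scores unused and so rest on a stronger missing-data assumption than the mean-change analysis of the same questionnaires

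*SAP*

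**What the plan says.** SAP 4.5 defines a progressor by a rise in score, for example "Proportion of patients who progress on the UCSD-SOBQ, as indicated by an increase in score of 10 points or greater" and "Proportion of patients who progress on the SGRQ total score, as indicated by an increase in score of 7 or greater". The three SGRQ domains have thresholds of 8 (Symptoms), 5 (Activity) and 7 (Impacts). The definitions give no rule for a missing score or for death. The method is one sentence: "The proportion of progressors at Week 52 will be estimated by treatment group with 95% CIs using a standardized regression estimator". Its closing words limit the covariates to two baseline variables: "adjusting for baseline score and baseline concurrent IPF treatment".

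On the population, SAP 4.1 says "All efficacy analyses will be performed on the FAS population, unless otherwise specified".

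For mean change in UCSD-SOBQ and SGRQ total, SAP 4.4.2.2 takes a different route: "The PRO secondary endpoints will be analyzed using the same estimand strategy, descriptive statistics and model as Hgb-corrected". The reference is to DLCO, whose model in SAP 4.4.2.1 is an MMRM on change from baseline at every visit, with baseline score, stratification factors, treatment, visit and their interaction. The estimand strategy is the primary one. SAP 1.1 describes it as follows: "All missing data, including data excluded after lung transplantations and missing data due to death, will be considered similar to data from other patients". The comparison is with patients who share the arm and the baseline characteristics.

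As I read the schedule in Protocol Appendix 1, the questionnaires are completed at baseline, Weeks 12, 24, 36 and 52, and at the treatment discontinuation visit. Protocol 2.1.3 had listed these endpoints as time to worsening. SAP Appendix 1 records only that the exploratory endpoints were simplified.

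**The concern.** A repeated-measures model and a single-timepoint regression make different use of a patient who leaves early. The MMRM is valid if missingness can be explained by baseline and by the scores already observed. The Week 52 regression needs missingness to be unrelated to Week 52 status given two baseline variables alone.

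Take a patient who is well past the threshold at Week 36 and then withdraws. The MMRM carries that information forward. The progressor analysis gives the patient the same probability as a completer who started from the same score. If worsening prompts withdrawal, the reported proportions come out too low, and the responder-type result no longer sits on the same footing as the mean-change result for the same questionnaire. The SAP does not acknowledge the difference.

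**Working it through.** **Plan's own figure.** There is none for these endpoints: no progressor rate, dropout rate or power is stated. Everything numerical below is an assumption.

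**Size of the effect, algebraically.** Assume a logistic model fitted in each arm to patients with a Week 52 score and averaged over all FAS patients in that arm. Let m be the share missing Week 52, p_miss their true progressor proportion, and p_pred the mean probability that the model predicts for them from baseline. The fitted model reproduces the completers' proportion, so

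shortfall = m × (p_miss − p_pred).

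With p_pred = 0.30:

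| m | p_miss 0.20 | 0.30 | 0.50 | 0.80 |
|---|---|---|---|---|
| 10% | −1.0 | 0 | 2.0 | 5.0 points |
| 20% | −2.0 | 0 | 4.0 | 10.0 points |

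The sign depends entirely on whether those missing progress more or less often than completers with the same baseline.

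**Simulation.** The inputs, all assumed, were:
- 200,000 patients per arm and scenario.
- Baseline score with mean 45 and SD 17; three equally likely concurrent-treatment groups.
- Mean 52-week change of +6 (placebo) and +3 (active), between-patient SD 11, measurement SD 6, and a slight negative dependence of Week 52 change on baseline.
- Threshold 7, as for SGRQ total.
- Log-odds of missing Week 52 rising with baseline score and, depending on the scenario, with the observed Week 36 change (coefficient 0, 0.5, 1.0 or −0.5 per 10 points), at base rates of 10% and 18%.

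Each cell is placebo / active, in %. All-patient status is Week 52 status had everyone been observed.

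| Missingness driven by | Missing | All-patient status | Planned estimator | Shortfall (points) | With Week 36 score added |
|---|---|---|---|---|---|
| Baseline only | 10.9 / 10.9 | 46.9 / 37.5 | 47.0 / 37.5 | −0.1 / 0.0 | 46.9 / 37.5 |
| Baseline only | 19.3 / 19.2 | 46.7 / 37.8 | 46.8 / 37.8 | −0.1 / 0.0 | 46.8 / 37.8 |
| Worsening | 13.9 / 12.6 | 47.0 / 37.6 | 45.2 / 36.0 | 1.8 / 1.6 | 47.0 / 37.6 |
| Worsening | 23.3 / 21.7 | 46.8 / 37.7 | 43.8 / 35.0 | 3.0 / 2.7 | 46.8 / 37.6 |
| Strong worsening | 18.8 / 16.2 | 47.0 / 37.3 | 42.6 / 33.5 | 4.4 / 3.8 | 47.0 / 37.3 |
| Strong worsening | 29.1 / 25.5 | 47.0 / 37.5 | 40.4 / 31.9 | 6.6 / 5.6 | 47.0 / 37.6 |
| Improvement | 9.8 / 10.7 | 47.0 / 37.7 | 48.2 / 38.9 | −1.2 / −1.2 | 47.0 / 37.7 |
| Improvement | 17.1 / 18.5 | 47.0 / 37.6 | 49.1 / 39.7 | −2.1 / −2.1 | 47.0 / 37.6 |

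**Arm difference.** In the four worsening rows the all-patient difference is 9.4, 9.1, 9.7 and 9.5 points. The planned estimator gives 9.2, 8.8, 9.1 and 8.5. The largest move is 9.5 − 8.5 = 1.0 point, against a largest shift in level of 6.6. Both arms share the same dropout mechanism here.

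**What the last column shows.** Using one interim score brings the estimate within 0.1 point. That is expected, because missingness was generated from the Week 36 score. The result confirms that the information lost is in data the trial collects; it does not show that real dropout behaves this way.

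**The case against.** Four points on the other side have weight.

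**The text is silent on missing scores, not wrong about them.** A reader might infer that patients who drop out or die are left out or scored as non-progressors. SAP 4.5 says neither, and standardising over the FAS gives each of them a predicted probability. Scoring them as non-progressors would have cost 5.9 to 17.8 points in the worsening rows (37.6 − 31.7 and 47.0 − 29.2), but the SAP does not specify that. This stands.

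**Downward bias is not established.** A reader might infer that both arms' proportions must be too low. The table shows no bias when missingness depends on baseline, and the reverse when improvers leave. Worsening-driven loss is plausible in a progressive disease, but neither document gives a rate or pattern. Protocol 4.6.1 encourages visits to Week 52 after study drug is stopped, so stopping drug need not mean a missing score. This also stands; the bias has to be stated conditionally.

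**Death is an estimand choice.** A reader might infer from SAP Table 7, where deaths in two endpoints are handled so that "they will be treated as disease progression and counted as event of interest", that deaths should count as progression here too. Those endpoints are adjudicated hospitalization and exacerbation. For these same questionnaires the mean-change analysis takes the hypothetical strategy, and counting deaths as progression would give one instrument two death rules. It also changes the quantity: with 3% to 9% deaths assumed, it raises the proportions by about 2 to 4 points, and that rise is redefinition, not bias. What remains is that SAP 4.5 does not say which strategy applies.

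**The assumption resembles the SAP's own.** SAP 1.1 also refers to patients with the same baseline characteristics, and status at Week 52 is not the same as having ever worsened. But the primary and PRO mean-change models condition on every observed visit, and this regression does not. The objection does not remove the mismatch.

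**Conclusion.** The point holds in a limited form. As written, the progressor analysis uses less of the collected data than the MMRM for mean change in SGRQ total and UCSD-SOBQ, and needs a stronger missing-data assumption. If dropout follows observed worsening, the proportions are too low by about 1.6 to 6.6 points per arm under the inputs above. If missingness depends on baseline only, there is no bias. The between-arm difference is affected less (up to about 1 point), provided dropout works the same way in both arms. These results assume a logistic model standardised over the FAS, and rates that are mine and not the documents'.

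The endpoints are exploratory and outside the testing sequence in SAP 4.4, so no confirmatory claim is at risk. This is a worthwhile refinement, with an omission (the death strategy) to close at the same time.

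**What to change.** In SAP 4.5, under the progressor analysis:

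1. For living patients with no Week 52 score, multiply impute it from a repeated-measures model using baseline and all post-baseline scores. The MMRM of SAP 4.4.2.2 serves for UCSD-SOBQ and SGRQ total; use the same form for the three SGRQ domains. Impute random draws, not predicted means, because a threshold applied to means would distort the proportions. Then apply the thresholds and the planned standardized estimator, and pool across imputations.
2. State the strategy for death. If it is the one already used for mean change in these questionnaires, say so.
3. Optionally, as a sensitivity analysis only, count death before Week 52 as progression, label it progression or death, and show deaths by arm beside it.

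The cost is a few sentences in the SAP and modest extra programming, with no new data collection. Items 1 and 2 do not depend on item 3.
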